1. PROTOCOL SYNOPSIS

Title:	WALTZ: a prospective, non-significant risk, feasibility study to evaluate serial 90-minute applications of VibratoSleeve therapy to acutely increase the perfusion in peripheral arterial disease (PAD) subjects 65 years of age and older.
Design:	Prospective, single arm, open-label clinical trial to evaluate the feasibility of TUS in the treatment of early stage (Rutherford Class 1-3) PAD. The results of this study will be used to support future studies.
Device Name and Intended Use:	VibratoSleeve is an array of single element ultrasound transducers, driven in a phased manner, and held in place externally by an adjustable sleeve. In this study, the VibratoSleeve will be applied in clinic and will be tested to demonstrate evidence of an increase in distal limb perfusion in adults with PAD.
Visit Schedule:	Visits will occur at screening (baseline data) and at three in-clinic treatment sessions, each separated by at least a 1-week interval.
Study Objectives:	The objectives of this study are: 
• To determine the feasibility of VibratoSleeve therapy to acutely increase distal perfusion in peripheral arterial disease (PAD) subjects 65 years of age and over.• Collect data on tolerable acoustic dose of serial 90-minute TUS therapy in the treatment of early stage (Rutherford Class 1-3) PAD.• Evaluate subject feedback on wearability and tolerability of serial 90-minute TUS therapy.• Evaluate the nature, incidence, timing and resolution of all adverse events in subjects treated with VibratoSleeve as compared with historical data on current standard of care treatments for PAD.
Number of Subjects and Defined Point of Enrollment	A total of up to 12 subjects will be required to receive VibratoSleeve therapy. The point of enrollment is defined as the time the subject signs the Informed Consent Form (ICF) to undergo screening procedures to ascertain eligibility. It is anticipated that up to 50% of subjects enrolled in the study will meet the inclusion/exclusion criteria. Given the screen success rate, it is anticipated that approximately 24 subjects could be enrolled in the study to have 12 evaluable subjects qualified for the treatment and evaluation.

Inclusion Criteria	
1. Age \geq 652. Diagnosis of PAD.3. Claudication symptoms in Rutherford class 1, 2, or 3 as determined by the investigator.
Exclusion Criteria	
1. Prior stenting in posterior tibial artery.2. Re-vascularization procedure within 30 days prior to enrollment in the study.3. Ulcers, cellulitis, or skin breakdown in treatment areas (posterior calf).4. History or diagnosis of severe chronic venous insufficiency.5. Acute limb ischemia within 30 days prior to treatment.6. History or diagnosis of deep venous thrombosis below the knee in treatment leg.7. Any conditions that, in the opinion of the investigator, may render the subject unable to complete the study or lead to difficulties for subject compliance with study requirements, or could confound study data.8. Subject's enrollment in another investigational study that has not completed the required primary endpoint follow-up period.
Safety Endpoint	All device and procedure related adverse clinical events experienced by subjects will be collected. Summaries of adverse events will be provided on a per subject and a per device basis. Severity and method of resolution will also be summarized. The number and primary reasons for medical or surgical interventions to treat device related adverse events will be summarized. This study is not powered to definitively evaluate the safety of the investigational device as compared to the historical data of comparable treatments for PAD.
Efficacy Endpoints	
The following parameters will be evaluated to assess performance of the VibratoSleeve TUS:
 
• The mean improvement in FlowMet perfusion rate as measured by the noninvasive FDA-approved imaging system FlowMet. Each subject's pre-treatment baseline perfusion rate will be calculated from at least 5 minutes (mean of 300 FlowMet measurements which are taken once a second) as Baseline period. The mean of the 90 minutes of the treatment period will then be normalized to the pre-treatment baseline to determine the percentage change in perfusion rate.• Tissue oxygen saturation and hemoglobin content as measured by the noninvasive FDA-approved imaging system Clarifi (StO₂). Clarifi measurements will be taken before (baseline), during and after treatment.

	
• Ankle and Toe Brachial Indices (ABI, TBI). Improvement in ABI, TBI will be similarly compared for all subjects. ABI and TBI will be taken before and after each treatment• Quality of Life with VascuQoL and Walking Impairment Questionnaires 
Mean changes of all these endpoints from baseline during the treatment and to post-treatment will be analyzed.

Treatment	
In this protocol, therapy will be delivered at VISOC clinic during 3 separate visits with at least 1-week interval between each visit. TUS therapy will last for 90 minutes during each treatment visit.
 
Each subject will receive either low, medium or high acoustic intensity (varying peak negative pressure) of TUS at a treatment visit and all subjects will receive all 3 levels of intensity during the study.
 
Regular monitoring will be conducted to ensure subject compliance with therapy during treatment.
 
Subjects will be discharged from the study after Treatment Visit 3 or until any device or procedure adverse events are resolved or remain stable.

Statistical Hypothesis	Statistical hypotheses will not be applied in this pilot study. Tables and descriptive statistics of the subject demographic data, treatment parameters, and outcome variables will be generated at the completion of the study. Information collected during the study may be used to support a 510(k) application as well as to select the endpoints and determine sample sizes for future trials.
Study Duration	The Sponsor expects the trial to last six months from the time the first subject enrolls until the time of the last visit.

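### The fourth objective covers all adverse events against historical data, but the safety endpoint commits to collecting only device- and procedure-related events

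*Protocol*

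**What the plan says.** All of the relevant text is in section 1 of the protocol, the synopsis.

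- **Study Objectives**, fourth item: every adverse event is to be evaluated "in subjects treated with VibratoSleeve as compared with historical data on current standard of care treatments for PAD". The scope is not limited to related events, and the comparator is historical.
- **Safety Endpoint**: "All device and procedure related adverse clinical events experienced by subjects will be collected". Summaries per subject and per device follow. The summary of interventions is restricted to device-related events.
- **Safety Endpoint**, last sentence: "This study is not powered to definitively evaluate the safety of the investigational device as compared to the historical data". Here the comparator is described as comparable treatments rather than current standard of care.
- **Visit Schedule** and **Treatment**: there are three sessions, at least one week apart. Subjects are discharged after the third, and follow-up continues beyond it only for device or procedure events.
- **Design** and **Number of Subjects**: "Prospective, single arm, open-label clinical trial to evaluate the feasibility of TUS"; "A total of up to 12 subjects will be required to receive VibratoSleeve therapy".
- **Statistical Hypothesis**: no hypotheses are applied and the output is descriptive. The information may support a 510(k) application and the planning of later trials.

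**The concern.** The objective and the endpoint that should serve it differ on which events count. The objective says all. The collection sentence says related, and the rules on interventions and on extended follow-up point the same way. A later analysis plan can define how recorded events are tabulated, but it cannot restore events that the trial did not collect.

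The historical clause raises the stakes. A related-only count over a short window could be set beside published rates with a different event definition and a longer window. Relatedness would also be judged in an open-label, single-arm setting, where everyone knows that the subject was treated. Because the results may be carried into a regulatory submission and later trials, a contrast of unlike quantities could travel beyond this study.

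**Working it through.** **1. The plan's own figure.** Inputs from Number of Subjects: 12 subjects to be treated and a screen success of 50%. 12 / 0.5 = 24, which matches the stated enrolment ("24 subjects could be enrolled"). The protocol gives no safety sample-size calculation and no historical rate, so there is nothing further to reproduce.

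**2. The passages side by side.**

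| Feature | Fourth objective | Safety Endpoint and Treatment |
|---|---|---|
| Events | all | device- and procedure-related |
| Interventions summarised | not restricted | for device-related events |
| Follow-up after the third session | timing and resolution of all events | only for device or procedure events |
| Comparator | standard-of-care treatments | comparable treatments |

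No sentence commits to recording unrelated events, so the objective cannot be met from the data that the endpoint describes.

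**3. Shortest observation window.** Three sessions have two gaps of at least 7 days, so 2 × 7 = 14 days from first to last treatment. This is a minimum, because no maximum gap is stated. For 12 subjects at the minimum, 12 × 14 / 365.25 = 0.46 person-years. With no events in that time, the one-sided 95% upper limit is −ln(0.05) / 0.46 = 2.996 / 0.46, or about 6.5 events per person-year.

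**4. Size of the scope mismatch (assumed inputs).** Let *p* be the true proportion of subjects with any adverse event and *s* the share judged related. The recorded proportion is then *p* × *s*. The protocol gives neither value. Taking *p* = 20%, with 12 × 0.20 = 2.4 subjects expected:

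| *s* | Recorded proportion | Expected subjects in 12 |
|---|---|---|
| 25% | 5% | 0.6 |
| 50% | 10% | 1.2 |
| 75% | 15% | 1.8 |

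This gap depends on what is counted. It would remain with any number of subjects.

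**5. Precision, which is a separate matter.** Exact limits with *n* = 12:

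- 0 of 12: two-sided 95% upper limit 1 − 0.025^(1/12) = 26.5%; one-sided 1 − 0.05^(1/12) = 22.1%.
- 1 of 12: Clopper-Pearson 95% interval 0.2% to 38.5%.
- Chance of seeing no event at an assumed true rate of 5%: 0.95^12 = 54%. At 10%: 0.90^12 = 28%.

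These limits show how little 12 subjects can say about a rate. They do not measure the mismatch in step 4, and widening collection does not change them.

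**The case against.** The best defence is that the protocol already concedes the point. It says that the study is not powered for this comparison, applies no hypotheses and reports descriptively. As to imprecision this stands, and small numbers alone would not be a finding in a feasibility study of up to 12 subjects. But the caveat speaks to precision. It does not address counting different events over a different period, and it leaves the comparative objective in place.

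A second defence is that the Safety Endpoint nowhere forbids recording other events, and its next sentence summarises adverse events without restriction. That is fair: related-only is the natural reading, not an express exclusion. The conflict still has to be resolved, because nothing commits the trial to the wider collection.

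Third, the source and window of the historical data may properly be left to the analysis plan. Their absence here is therefore not criticised. It matters only because it leaves the direction of any bias unknown.

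A reader might infer several stronger things that the text does not support:

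- *The comparison is biased toward the device.* This follows only if the historical data count events of any cause or cover longer follow-up. If they count treatment-related events over a similar window, the scope bias disappears.
- *Follow-up is about two weeks.* That is the minimum; follow-up may be longer, and it is extended for unresolved device or procedure events.
- *Twelve subjects could not be distinguished from any historical rate.* With no events, rates above 26.5% would lie outside the two-sided interval.
- *The trial will conclude that the device is safer.* No sentence says that such a conclusion will be drawn.

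**Conclusion.** The point holds as an internal contradiction. The fourth objective names all adverse events, the Safety Endpoint commits to related events only, and follow-up is extended only for device or procedure events. Followed as written, the trial cannot deliver the all-event incidence that it sets out to evaluate, and this loss cannot be repaired at analysis.

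The size of any distortion in a historical contrast cannot be fixed from the protocol. On the assumed values above, a 20% all-event rate would be recorded as 5% to 15%. The direction favours the device only if the historical data are broader in scope or longer in follow-up. The feasibility aims and the sample size are not affected. The correction should be made before enrolment, since it concerns what is recorded.

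**What to change.** - **Safety Endpoint:** reconcile it with the objective by collecting all adverse events at the visits already planned, with relatedness to device and procedure recorded for each. Related events can still be summarised as a subset.
- **Fourth objective:** delete the clause on historical standard-of-care data. Alternatively, limit it to a descriptive contrast with events defined in the same way over a similar window.
- **Reporting:** give the number and proportion of treated subjects with an event, with exact 95% intervals, and draw no comparative safety conclusion.
- **Keep** the statement that the study is not powered for this comparison. It is correct and useful.

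The cost is a wording change plus slightly more event recording at existing visits. The sample size and visit schedule do not change. What is given up is a comparative safety claim, which this design could not support.

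### Does an anticipated enrolment of about 24, worked out from a 50% ceiling on eligibility, leave the trial short of its 12 subjects?

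*Protocol*

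**What the plan says.** Everything that bears on the enrolment figure is in the Protocol Synopsis.

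- **Number treated** (Number of Subjects and Defined Point of Enrollment): "A total of up to 12 subjects will be required to receive VibratoSleeve therapy".
- **When a subject counts as enrolled** (same row): "The point of enrollment is defined as the time the subject signs the Informed Consent Form (ICF) to undergo screening procedures to ascertain eligibility". Enrolment is therefore a count of consents, and screen failures are included in it.
- **Screen success** (same row): "It is anticipated that up to 50% of subjects enrolled in the study will meet the inclusion/exclusion criteria".
- **Resulting forecast** (same row): the sponsor anticipates that approximately "24 subjects could be enrolled" "in the study to have 12 evaluable subjects qualified for the treatment and evaluation".
- **Exposure** (Treatment row): "therapy will be delivered at VISOC clinic during 3 separate visits with at least 1-week interval between each visit", and "all subjects will receive all 3 levels of intensity during the study".
- **Analysis** (Statistical Hypothesis row): no hypotheses are tested. The results are tables and descriptive statistics, which may support a regulatory application and help to choose endpoints and sample sizes for later trials.

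**The concern.** Two features of the enrolment row look wrong on a first reading.

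1. The eligibility rate is given as an upper limit, yet the enrolment number is the target divided by that limit. If 50% is the highest rate foreseen, 24 is the lowest enrolment that could give 12 eligible subjects on average. Any lower rate gives fewer.
2. The number 12 is both the most who may be treated and the number wanted as evaluable. A full record needs three visits at least a week apart, because each visit delivers one intensity. If evaluable meant completing all three visits, 12 evaluable out of at most 12 treated would allow no loss at all, and the enrolment sum has no term for loss.

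If both points held and consenting stopped at 24, the study could end with fewer than 12 subjects seen at all three intensities. The descriptive estimates would then be less precise, and so would any later sample-size calculation built on them.

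**Working it through.** **Inputs from the Protocol Synopsis:** target 12; screen success at most 50%; forecast about 24 consents; three visits per subject.

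**Inputs that are assumed:** eligibility of 45%, 40% or 30%; loss of 5%, 10% or 20% per subject over the three visits; a 90% assurance standard; a hard stop at 24 consents. None of these is in the Protocol.

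**Step 1. The plan's own figure.** Consents = target / success rate = 12 / 0.50 = 24. The stated figure is reproduced exactly, with no loss term.

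**Step 2. Lower eligibility, no loss.** With success rate p, consents for an average of 12 are 12/p, rounded up. The average yield from 24 is 24p. If consenting stopped at exactly 24, the chance of at least 12 eligible is the binomial tail P(X ≥ 12) with n = 24.

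| p | 12/p, rounded up | 24p | P(X ≥ 12), n = 24 |
|---|---|---|---|
| 0.50 (stated ceiling) | 24 | 12.0 | 0.58 |
| 0.45 (assumed) | 27 | 10.8 | 0.38 |
| 0.40 (assumed) | 30 | 9.6 | 0.21 |
| 0.30 (assumed) | 40 | 7.2 | 0.03 |

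For 90% assurance of at least 12 eligible, the smallest n is 31 at 50%, 34 at 45% and 39 at 40%.

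**Step 3. Loss over three visits, if evaluable meant completing all three.** At 50% eligibility and loss d, consents for an average of 12 completers are 12 / (0.50 × (1 − d)).

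- d = 5%: 12/0.475 = 25.3, so 26. The average from 24 is 11.4, and P(X ≥ 12) = 0.48.
- d = 10%: 12/0.45 = 26.7, so 27. The average from 24 is 10.8, and P(X ≥ 12) = 0.38.
- d = 20%: 12/0.40 = 30. The average from 24 is 9.6, and P(X ≥ 12) = 0.21.

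If exactly 12 start, all 12 complete with probability 0.95^12 = 0.54 at 5% loss and 0.90^12 = 0.28 at 10% loss.

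**Step 4. What these results depend on.** The sums are correct, but each shortfall needs a premise that the Protocol does not supply.

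- The tail probabilities need consenting to end at 24. The Synopsis sets no such limit: the number is anticipated, approximate and conditional in its verb. Without a limit, lower eligibility shows up in the second column of the table (more consents), not in the last.
- The figures of 31, 34 and 39 need a 90% assurance standard, which the Protocol does not set.
- Step 3 needs evaluable to mean completing three visits. The text links it to being "qualified" in the screening sense: the wording is "to have 12 evaluable subjects qualified for the treatment and evaluation". If a subject with one usable session counted as evaluable, loss between visits would not reduce the count.
- A shortfall matters only against a required minimum. The treated number is a maximum, so 10 or 11 treated subjects is within the plan.

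**The case for a change.** The best case for a change is that the mismatch can be seen in the text without any outside figure. A ceiling on a rate is not an expected rate, and dividing by it gives the smallest possible answer. Because enrolment counts from consent, 24 is also the number of people the sponsor tells others it expects to consent, so a realistic figure or range would be more informative. The data may feed a regulatory application and later sample sizes, and in a study with no test the number of complete subjects sets the precision. The edit would be wording only.

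Part of this stands. 24 is a best-case average, and a reader who took it as a firm limit would be misled. The Protocol also leaves open whether evaluable means qualified, treated or completed.

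The rest does not carry. At the only rate the Protocol gives, 24 consents yield 12 on average, so it is too strong to say that 24 fails to deliver 12. That the trial will probably finish short follows only from a stop at 24 combined with lower eligibility or loss among completers. Exclusion criterion 7 already lets the investigator leave out subjects thought unable to complete the study, which lessens the loss question though it does not remove it. The definition of evaluable, replacement of subjects and the handling of incomplete records are commonly settled in the statistical analysis plan, which is not at hand.

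**Conclusion.** No change to the plan is needed. The row is loosely worded: it uses a ceiling as a planning rate, and the cost is a recruitment forecast that may be low. Its size is about 3 extra consents if success is 45% (27 against 24) and 6 if it is 40% (30 against 24), both assumed rates. Staff would meet this by screening somewhat longer or by treating slightly fewer than the maximum of 12, and the plan allows either.

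No result changes. There is no hypothesis, power or precision target tied to 12, and the descriptive summaries are equally valid with 10, 11 or 12 treated subjects. They are only a little less precise with fewer.

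The conclusion rests on two readings of the Synopsis: that 24 is a forecast and not a cap, and that 12 is a maximum and not a required minimum. The wording supports both. If a document not shown here fixed 24 as a hard limit and also required 12 completers, the shortfall figures above would apply.

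### The safety objective covers all adverse events in treated subjects, but the only collection sentence names device- and procedure-related events

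*Protocol*

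**What the plan says.** All of the text is in section 1, Protocol Synopsis.

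- **Study Objectives**, fourth item: "Evaluate the nature, incidence, timing and resolution of all adverse events in subjects treated with VibratoSleeve as compared with historical data", the historical data being those on current standard-of-care treatments for PAD.
- **Safety Endpoint**, first sentence: "All device and procedure related adverse clinical events experienced by subjects will be collected". This is the only statement at hand of what is recorded.
- **Safety Endpoint**, next sentences: "Summaries of adverse events will be provided on a per subject and a per device basis" and "Severity and method of resolution will also be summarized", neither of them limited by relationship. Then a limited one: "The number and primary reasons for medical or surgical interventions to treat device related adverse events will be summarized".
- **Treatment**, last paragraph: the discharge rule ties any follow-up past Treatment Visit 3 to adverse events of the device or procedure.
- **Design**: "Prospective, single arm, open-label clinical trial to evaluate the feasibility of TUS".

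The Safety Endpoint row also states that the study lacks the power for a definitive safety comparison with historical data.

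**The concern.** The objective and the collection rule cover different sets of events. Related events are a subset of all events, so data gathered under the literal rule need not supply what the objective asks for.

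Three things follow if a site reads the rule literally:

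- The all-event incidence, timing and resolution named in the objective cannot be tabulated. A later analysis plan can choose among recorded events, but it cannot restore events that were never written down.
- The judgement of relatedness decides whether an event enters the data at all. In a single-arm, open-label study no concurrent group can inform that judgement, and an event judged unrelated and left out cannot be reviewed afterwards.
- Related-event incidence put in place of all-event incidence can err in one direction only, downward. The objective sets incidence beside historical data, so this bears on how that comparison would look.

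**Working it through.** The point is textual, so the check sets the rows side by side.

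| Row of the synopsis | Function | Events covered |
|---|---|---|
| Study Objectives | What is to be evaluated | All, in treated subjects |
| Safety Endpoint, sentence 1 | What is collected | Device- and procedure-related |
| Safety Endpoint, sentences 2 and 3 | What is summarized | Adverse events, no qualifier |
| Safety Endpoint, sentence 4 | Summary of interventions | Device-related |
| Treatment, discharge rule | What is followed past Treatment Visit 3 | Device or procedure events |

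**Step 1. Does the collection rule supply the objective?** Taken literally, no. It names a subset of the events that the objective names.

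**Step 2. Does other text close the gap?** The unqualified summary sentences do not, because a summary can cover only what was collected. The intervention sentence and the discharge rule both fit the narrow reading. Nothing at hand says that unrelated events are recorded.

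**Step 3. Which way would an error run?** Let A be the number of treated subjects with at least one adverse event of any kind, and R the number with at least one related event. Every subject counted in R is also counted in A, so R ≤ A. With n treated subjects (up to 12), R/n ≤ A/n. The two are equal only if no treated subject had unrelated events alone.

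**Step 4. How large is A − R?** The document gives no event rate, related or unrelated, so the difference cannot be computed. It may be zero.

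**Step 5. What would a wider collection window involve?** The plan's own enrollment figure reproduces: 12 / 0.50 = 24. Of about 24 enrolled subjects, about 24 − 12 = 12 would never be treated. The objective is limited to treated subjects, so it does not require all-event collection in those 12. This figure bears only on the optional part of the fix.

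**The case against.** The strongest reply is that no loss of events has been shown. Only the synopsis is at hand. The sentence is a row in a summary table, not an instruction to sites, and a fuller safety section or form instruction may exist. The sentence contains no exclusion, and the unqualified summaries that follow leave the wider reading open. The study treats up to 12 subjects, applies no statistical hypotheses and disclaims power for safety. There are also two ways to restore consistency, and choosing the broader one is a judgement about how much safety data a small feasibility study should gather.

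Much of this stands. Loss of events is possible, not demonstrated, and the stakes are low. What does not fall away is the mismatch itself: the wider reading is possible but nowhere stated, and a fuller section elsewhere would still leave the synopsis sentence needing correction. The power disclaimer concerns precision, not completeness of recording.

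Two stronger readings are tempting, and the document supports neither.

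- A reader might infer that most events would be lost, because three 90-minute sessions fill only a small part of the weeks they span. But the rule filters on relatedness, not on time. A related event that arises between visits is covered, so time outside the sessions does not measure what would be missed.
- A reader might infer that every event must be collected from consent, because "The point of enrollment is defined as the time the subject signs the Informed Consent Form (ICF) to undergo screening procedures to ascertain eligibility". That fixes enrollment, not the period of the safety objective, which concerns treated subjects.

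**Conclusion.** The contradiction between the Study Objectives row and the Safety Endpoint row is real, and no other text at hand resolves it. Followed literally, the collection rule could leave part of a stated objective unanswerable and would let an open-label judgement of relatedness decide what is recorded. The direction is fixed: related-event incidence equals or understates all-event incidence. The size is not quantifiable from the document and may be zero.

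The consequence rests on two assumptions: that a site applies the collection sentence as written, and that no fuller collection rule stands elsewhere. No test, sample size or efficacy endpoint depends on the point. It should be fixed, at low weight.

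**What to change.** 1. Reword the collection sentence in the Safety Endpoint row, for example: *All adverse events in treated subjects, at least from first treatment to study exit, will be collected regardless of relationship; relationship to device and to procedure, severity, onset and resolution status will be recorded for each.*
2. Keep collection of device- and procedure-related events before first treatment as now stated. Extending all-event collection back to ICF signature is optional. If that is done, list events before first treatment, and those of never-treated subjects, separately from the tables that answer the objective.
3. Report all-cause and related events separately, and say which set each summary in the Safety Endpoint row uses.
4. Reconcile the Study Objectives, Safety Endpoint and Treatment rows on which events are collected, summarized and followed.

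With relatedness held as an attribute, both sets can be tabulated; from related events alone, the full set cannot be rebuilt. The alternative is to narrow the objective to related events. That also makes the text consistent, but gives up the all-event information.

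**Cost.** Changed wording and a little more event recording, including events that arise between visits, with no extra subjects or visits. The reported event rate may look less favourable. The optional start at ICF signature would add recording for about 12 enrolled but untreated subjects.

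### Must the sentence promising during-treatment and post-treatment changes for every efficacy endpoint be rewritten because only half of those changes have a stated measurement?

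*Protocol*

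**What the plan says.** All the relevant text is in Protocol section 1, Protocol Synopsis. The Efficacy Endpoints row lists four items with these times:

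- **FlowMet perfusion.** The "pre-treatment baseline perfusion rate will be calculated from at least 5 minutes (mean of 300 FlowMet measurements which are taken once a second"); then "The mean of the 90 minutes of the treatment period will then be normalized to the pre-treatment baseline" to give a percentage change.
- **Clarifi oxygen saturation and hemoglobin.** "Clarifi measurements will be taken before (baseline), during and after treatment".
- **ABI and TBI.** "ABI and TBI will be taken before and after each treatment". Improvement is to be compared in the same manner as for the preceding endpoints.
- **Questionnaires.** Listed only as "Quality of Life with VascuQoL and Walking Impairment Questionnaires", with no time.

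The row ends with the general statement "Mean changes of all these endpoints from baseline during the treatment and to post-treatment will be analyzed".

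Two other rows bear on the point. Visit Schedule says "Visits will occur at screening (baseline data) and at three in-clinic treatment sessions, each separated by at least a 1-week interval". Treatment says that "all subjects will receive all 3 levels of intensity during the study", with discharge after the third treatment visit unless an adverse event is still open. Statistical Hypothesis states that no hypotheses are tested and that results are summarized descriptively, possibly to support a 510(k) application and to plan later trials.

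**The concern.** The closing sentence covers every endpoint and both changes, yet the times listed just above it do not cover every combination. ABI and TBI have no reading during the session. No FlowMet window after switch-off is given. The questionnaires have no time at all, and because no visit is scheduled after the third session, any questionnaire following that session would be same-day.

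The word baseline adds to the doubt. Visit Schedule attaches it to screening, while the FlowMet and Clarifi items attach it to the period before a session. The two could give different answers. By the third treatment visit a screening value would be at least 2 × 7 = 14 days old, and the subject would already have received the other two intensities.

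If these gaps were real, some would be permanent: a statistical analysis plan can choose among recorded values but cannot create a reading that nobody took. Later trials might then be planned from mean changes and variances whose two time points are unclear.

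**Working it through.** There is no stated figure to reproduce on this point, so the check is a count followed by a reading of each gap.

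**Step 1: the count.** Four endpoints × 2 promised changes = 8.

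| Endpoint | During treatment | After treatment |
|---|---|---|
| FlowMet | stated | not stated |
| Clarifi | stated | stated |
| ABI/TBI | conflicts with stated times | stated |
| Questionnaires | not stated | not stated |

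Stated: 1 + 2 + 1 + 0 = 4 of 8. Counting single measures (FlowMet, oxygen saturation, hemoglobin, ABI, TBI and the two questionnaires) gives 1 + 2 + 2 + 1 + 1 + 0 + 0 = 7 of 14, again half. If the phrase about treatment meant the whole three-visit course, ABI/TBI would be covered and the count would be 5 of 8. That reading fits poorly, because the FlowMet item uses the treatment period for the 90-minute session.

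**Step 2: what kind of gap each is.** Of the 8 − 4 = 4 unmet cells, 1 is a conflict (ABI/TBI during treatment) and 3 are silence. Nothing says that FlowMet recording stops at switch-off or that the questionnaires are given only once. Only the synopsis is at hand, and these times are of the kind that a fuller schedule or the analysis plan supplies.

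**Step 3: which baseline.** The closing sentence belongs to the same row as the endpoint items. There, baseline is the pre-session value by name for FlowMet and Clarifi, and by the pairing of before and after readings for ABI/TBI. The screening wording in Visit Schedule labels a visit; it does not define a comparator for change. One could set 12 × 1 = 12 screening values against 12 × 3 = 36 pre-session values for 12 treated subjects. That contrast, like the 14-day interval, assumes efficacy measures are taken at screening, and no text says they are. The doubt is left only for the questionnaires.

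**Step 4: the FlowMet baseline length.** One reading per second for 5 minutes is 5 × 60 = 300 readings. Five minutes as a minimum recording and 300 as the number averaged are compatible. Which 300 to use from a longer recording is ordinary analysis-plan detail.

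**Step 5: what the analysts would do.** Taking the text as it stands:

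- FlowMet: the 90-minute mean relative to the pre-session value.
- Clarifi: changes during and after the session.
- ABI/TBI: change from before to after each session, with no during-treatment entry.
- Questionnaires: summaries at whatever times they were given, labelled with those times.

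None of these results would be wrong because of the closing sentence.

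**The case for a change.** The strongest case for a change is that timing is decided at the visit and not at analysis. If nobody writes down when the questionnaires are given, or whether the FlowMet sensor stays on after switch-off, the data may be lost for good. The ABI/TBI item is a true mismatch, the results may inform the endpoints and sample sizes of future trials, and the repair is mostly wording with no extra visit.

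Part of this stands. The closing sentence does claim more than the ABI/TBI schedule can deliver, and the questionnaires have neither a time nor a baseline in the text shown. If the protocol were amended for another reason, tidying both would be harmless.

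The rest does not carry. That an analysis plan cannot recover missing readings is true in general, but nothing here shows that any reading will be missed. Same-day assessment after the third session contradicts nothing in a study whose stated objective is an acute rise in perfusion. A fixed FlowMet window after switch-off, or a set start time for the baseline recording, would be a preference about data collection and not the correction of a shown error. Describing the questionnaire change as running from screening to a named visit would assume that they are given at screening, and at a later visit could mix in effects of earlier sessions at other intensities.

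**Conclusion.** No change follows. The closing sentence is loosely worded: 1 of its 8 literal promises conflicts with the schedule and 3 are untimed in a synopsis. The conflicting promise has an obvious resolution, because ABI and TBI can only be reported from before to after each session. The FlowMet percentage change is computable as written, as are both Clarifi changes. With no hypothesis test and no decision rule, the loose wording moves no error rate, power or sample size, and no bias in any reported summary has been shown.

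This rests on two assumptions: that the detailed schedule or the analysis plan, neither of which is shown, gives the questionnaire times, and that each reported change is labelled with its two time points. If a full schedule turned out to give the questionnaires at only one time, no questionnaire change could be computed, and the point would deserve another look for that endpoint alone.
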